It is the responsibility of the investigator, or a person designated by the investigator (if acceptable by local regulations), to obtain written informed consent from each individual participating in this study after adequate explanation of the aims, methods, objectives and potential hazards of the study. It must also be explained to the subjects that they are completely free to refuse to enter the study or to withdraw from it at any time for any reason. Appropriate IRB-approved forms for obtaining written informed consent will be provided by the investigator or by Regenesis Biomedical, Inc. or their designee.

If new safety information results in significant changes in the risk/benefit assessment, the consent form will be reviewed and updated if necessary. All subjects (including those already being treated) will be informed of the new information, given a copy of the revised form and be re-consented to continue in the study.

VIII. INSTITUTIONAL REVIEW BOARD

This protocol, the informed consent form and any accompanying material provided to the subject (such as subject information sheets or descriptions of the study used to obtain informed consent) as well as any advertising or compensation given to the subject, will be submitted by the investigator or investigator's designee to an IRB. Approval from the IRB must be obtained before starting the study and will be documented in a letter to the investigator specifying the date on which the IRB met and granted the approval.

IX. TERMINATION OF THE INVESTIGATION

As the study sponsor, Regenesis Biomedical, Inc. reserves the right to terminate the study at any time. Should early termination be necessary, Regenesis Biomedical, Inc. and the investigator will consult and make sure that adequate consideration is given to the protection of subjects' interests.

Additionally, data will be reviewed by the sponsor on a regular basis. Reports of data will be made available to the Institutional Review Boards and to the FDA as required. Unanticipated adverse device events will be evaluated and reported in accordance with 21 CFR Part 812 requirements and as required by the governing IRB.

This study will be suspended if the investigator or the sponsor, upon review and evaluation of the clinical data, finds the severity or incidence of single or total adverse events unacceptable for continuation of the investigation.

X. ADVERSE EVENTS AND UNANTICIPATED ADVERSE DEVICE EFFECTS

A. Adverse Events

An adverse event is defined as follows: Any untoward medical occurrence in a patient or clinical investigation patient administered a medical device treatment which does not necessarily have to have a causal relationship with this treatment. An AE can therefore be any unfavorable and unintended sign (including an abnormal laboratory finding), symptom, or disease temporally associated with the use of study device treatment, whether or not considered related to the study device.

All AEs occurring after signing of the consent form will be recorded. AEs arising subsequent to the time of initiation of first treatment with study device will be considered treatment emergent AEs.

At each contact with the subject, the investigator or designee must seek information on AEs by non-leading specific questioning and, as appropriate, by examination. All observed or volunteered AEs, regardless of suspected causal relationship to study device, must be recorded in the patient's chart.

Any events involving illnesses or injuries with onset during the study or any events involving exacerbations of pre-existing illnesses should be recorded. All clearly related signs and symptoms should be grouped together and recorded as a single diagnosis in the patient's chart. A pre-existing condition must not be reported as an AE unless the condition worsens during the trial.

Each AE will be independently judged by the investigator in terms of causality. The following definitions will be used for these causality assessments.

- | | |
|--------------------------|--|
| Related: | This causal relationship is assigned when the AE: 
 • starts a reasonable time after study device administration, • cannot be reasonably explained by the subject's clinical state. |
| Possibly Related: | This causal relationship is assigned when the AE: 
 • starts a reasonable time after study device administration, but • could have been produced by the subject's clinical state or other modes of therapy administered to the subject. |
| Unrelated: | This causal relationship is assigned when the AE: 
 • is definitely not associated with the study device administered and is readily explained by other events or diagnoses. |

Each AE will also be independently judged by the investigator in terms of severity. The following definitions will be used for these severity assessments.

- | | |
|------------------|--|
| Mild: | The event is transient (<48 hours) or causes mild discomfort; no medical intervention/therapy is required |
| Moderate: | The event results in mild to moderate limitation in activity – some assistance may be needed; no or minimal medical intervention/therapy is required |

Severe: The event results in marked limitation in activity, assistance is usually required; medical intervention/therapy is required and hospitalization is possible

Each AE will also be independently judged by the investigator in terms of seriousness. A serious adverse event (SAE) is defined as any untoward medical occurrence that:

- Results in death, or
- Is life-threatening,

Note: The term “life-threatening” in the definition of “serious” refers to an event in which the subject was at risk of death at the time of the event; it does not refer to an event which hypothetically might have caused death if it were more severe.

- Requires inpatient hospitalization or prolongation of existing hospitalization,
- Results in permanent impairment of a body function or permanent damage to a body structure,
- Is a congenital anomaly/birth defect,
- Necessitates medical or surgical intervention to preclude any one of the outcomes listed in this definition.

All SAEs must be reported *immediately* (within 24 hours of knowledge of the event) by telephone and fax to the following:

Sponsor Medical Contact – [name]; Regenesi Biomedical Inc.

[contact]; [contact]; [contact]

The investigator will follow up with a written description of the SAE submitted to the sponsor within 3 days, including the results of the SAE investigation and any treatment(s) provided.

All adverse events will be followed until resolution or until the investigator assesses the subject’s status has returned to normal.

B. Anticipated Adverse Device Effects Associated with Provant

Anticipated adverse events associated with Provant, reported at least once since market launch in 2004, are as follows:

- Device fails to operate
- Warmth or burning at treatment site
- Skin reaction at treatment site (tingling, pins-and-needles, rash, blisters, swelling, dry skin, redness, numbness, sensation of warmth)
- Increased bleeding at surgical site
- Chilliness
- Headache
- Malaise
- Nausea

- Abdominal or chest wall discomfort
- Muscle cramps
- Failure to reduce pain or an increase in pain
- Metallic taste in mouth
- Exacerbation of tinnitus
- Stiffness
- Weakness
- Dizziness/lightheadedness
- Restless leg syndrome
- Strong urine odor
- GI/upset stomach
- Excessive menstruation

C. Unanticipated Adverse Device Effect (UADE)

Unanticipated Adverse Device Effect means any serious adverse effect on health or safety or any life-threatening problem or death caused by, or associated with, a device, if that effect, problem, or death was not previously identified in nature, severity, or degree of incidence in the protocol or informed consent form, or any other unanticipated serious problem associated with the device that relates to the rights, safety, or welfare of subjects.

All UADEs must be reported *immediately* (within 24 hours of knowledge of the event) by telephone and fax to the following:

Sponsor Medical Contact – [name]; Regenesis Biomedical Inc.;
[contact]; [contact]; [contact]

The investigator will follow up with a written description of the UADE submitted to the sponsor within 3 days, including the results of the UADE investigation and any treatment(s) provided.

Any UADE occurring up to the date of the final Follow-up Visit will be followed until it resolves, the investigator assesses the subject's status to have returned to baseline, or until the investigator feels that the event is stable and chronic.

The investigator shall submit to the reviewing IRB a report of any UADE occurring during an investigation as soon as possible in accordance with the IRB submission guidelines, but in no event later than 10 working days after the investigator first learns of the effect.

XI. INVESTIGATOR'S FILES/RETENTION OF DOCUMENTS

The investigator must maintain adequate and accurate records to enable the conduct of the study to be fully documented and the study data to be subsequently verified. These documents should be classified into two different separate categories (1) Investigator's Study File, and (2) Subject clinical source documents. The Investigator's Study File will contain the protocol/amendments, data collection forms, Independent Ethics Committee/Institutional Review Board and governmental approval with correspondence, sample informed consent, device records, staff curriculum vitae and

authorization forms and other appropriate documents/correspondence. All records defined in 21 CFR 812.140 will be kept on file.

Subject clinical source documents include subject hospital/clinic records, physician's and nurse's notes, appointment book, original lab reports, special assessment reports, signed informed consent forms, subject screening and enrollment logs.

The investigator must keep these two categories of documents on file for at least 2 years after the latest of the following: completion, discontinuation of the study, or the regulatory submission for which the study is being performed is no longer under review. After that period of time the documents may be destroyed, subject to local regulations.

Should the investigator wish to assign the study records to another party or move them to another location, Regenesys Biomedical, Inc. must be notified in advance.

If the investigator cannot guarantee this archiving requirement at the investigational site for any or all of the documents, special arrangements must be made between the investigator and Regenesys Biomedical, Inc. to store these in a sealed container(s) off-site so that they can be returned sealed to the investigator in case of a regulatory audit. Where source documents are required for the continued care of the subject, appropriate copies should be made for storing outside of the site.

A. Source Documents and Background Data

The investigator shall supply the sponsor on request with any required background data from the study documentation or clinic records. This is particularly important when data requires clarification. In case of special problems/and or governmental queries or requests for audit inspections, it is also necessary to have access to the complete study records, provided that subject confidentiality is protected.

All forms should be typed or filled out using indelible ink, and must be legible. Errors should be crossed out but not obliterated, the correction inserted, and the change initialed and dated by the investigator or his/her authorized delegate.

B. Audits and Inspections

The investigator should understand that source documents for this trial should be made available to appropriately qualified personnel from the Regenesys Biomedical, Inc. Quality Assurance Unit or its designees or to health authority inspectors after appropriate notification. The verification of the data must be by direct inspection of source documents and patient charts.

XII. MONITORING THE STUDY

It is understood that the responsible Regenesys Biomedical, Inc. monitor (or designee) may contact and visit the investigator and will be allowed, upon request, to inspect the various records of the trial provided that subject confidentiality is maintained in accord with local requirements.

If a monitoring visit is scheduled, the monitor may inspect the patient charts for completeness, consistency and accuracy of the data captured. The monitor should have access to laboratory test reports and other subject records needed. The investigator (or his/her designee) agrees to cooperate with the monitor to ensure that any problems detected in the course of these monitoring visits are resolved.

XIII. CONFIDENTIALITY OF TRIAL DOCUMENTS AND SUBJECT RECORDS

The investigator must assure that subjects' anonymity will be maintained and that their identities are protected from unauthorized parties. On documents submitted to the sponsor, subjects should not be identified by their names, but by an identification code. The investigator should keep a subject enrollment log showing codes, names and addresses. The investigator should maintain documents not for submission to Regenesis Biomedical, Inc., e.g., subjects' written consent forms, in strict confidence.

XIV. PUBLICATION OF DATA AND PROTECTION OF TRADE SECRETS

The results of this study may be published or presented at scientific meetings. If this is foreseen, the investigator agrees to submit all manuscripts or abstracts to Regenesis Biomedical, Inc. at least 30 days prior to submission. This allows the sponsor to protect proprietary information and to provide comments based on information from other studies that may not yet be available to the investigator.

In accordance with standard editorial and ethical practice, Regenesis Biomedical, Inc. will generally support publication of multicenter trials only in their entirety and not as individual center data. In this case, a coordinating investigator will be designated by mutual agreement. Any formal publication of the study in which input of Regenesis Biomedical, Inc. personnel exceeded that of conventional monitoring will be considered as a joint publication by the investigator and the appropriate Regenesis Biomedical, Inc. personnel. Authorship will be determined by mutual agreement.

XV. REFERENCES

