Outcome measures of response to treatment with Provant will be determined based on the location of the subject's treatment area. Protocol required assessments will include baseline and interim / end of treatment visit and 3-month follow-up (post-treatment) pain scores using an 11-point numeric pain rating scale (NPRS), and a Clinical Global Impression – Global Improvement (CGI-I) Scale and a Patient Global Impression of Change (PGIC) Scale. All outcome measures administered as part of non-invasive standard of practice assessments will be collected, e.g., pain scores, SF-36, ankle-foot scales, oxygen perfusion (MOXY), and diaries with some subjects.

2. Safety Assessments

Safety will be assessed through review of AE reports and concomitant treatments and medications. All concomitant drug or non-drug treatments used will be recorded. Safety outcomes will be assessed at office visits as defined by the treatment regimen.

IV. STUDY PROCEDURES

The study procedures are summarized in the Schedule of Events (Appendix A) and described immediately following:

A. Visit 1 – Screening Visit (Day -14 to 0)

The Screening Visit will take place no more than 14 days prior to the Enrollment Visit. If a successfully screened subject falls out of the 14-day limit, the subject will require another screening to participate. The following procedures will be performed:

1. Informed consent review and signature.
2. Review Inclusion and Exclusion criteria.
3. Collect subject demography data (including age, weight, height, gender, and race/ethnicity).
4. Collect Medical and Surgical History.
5. Review and record all concomitant medications.
6. Perform a urine pregnancy test for females of child bearing potential.
7. If the subject meets the eligibility criteria, continue on to the Enrollment Visit.

If subject does not require any washout for prohibited medications or procedures, the Screening Visit and the Enrollment Visit can be conducted concurrently.

B. Visit 2 – Enrollment Visit (Day 0)

The following procedures will be performed:

1. Review Inclusion/Exclusion criteria (if Screening/Enrollment visits not combined).

2. Review and record any changes in medical history and study eligibility criteria since screening (if Screening/Enrollment visits not combined).
3. Review and record adverse events (if Screening/Enrollment visits not combined).
4. Review and record any changes in concomitant medications (if Screening/Enrollment visits not combined).

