5. Conduct baseline efficacy assessments.

Response to treatment with Provant will be determined based on the location of the subject's treatment area. Assessments will include the NPRS and non-invasive assessments part of the investigator's standard of practice e.g., pain scores, SF-36, ankle-foot scales, oxygen perfusion (MOXY), and diaries with some subjects.

6. If the subject continues to meet eligibility criteria, enroll subject, and dispense study device.
7. Introduce and train the subject on the use of the Provant Therapy System, including instructions for proper positioning and operation of the device.
8. If applicable, distribute a patient diary and instruct the subject on how to complete. Examples of diary collection tools are provided in Appendix B.

During this visit, eligible subjects will receive a Provant device and up to 120 Disposable Applicator Covers (packs of 30, depending on the anticipated treatment duration) and the subject will be instructed to administer treatment as prescribed by the investigator.

C. Treatment Period

Treatment may be self-administered by the subject, or with the assistance of a family member or caregiver. Subjects will assume a comfortable position and place the treatment applicator pad of the Provant device centering the applicator pad on the treatment location as instructed by the investigator. Treatment will be administered for 30 consecutive minutes.

Subjects will be asked to complete the patient reported outcome form(s) as instructed (as applicable).

D. Interim Visits

Subjects will be required to return to the clinic during the course of treatment as instructed by the investigator. Telephone follow-ups may also be performed with each subject as determined by the investigator. At these interim visits, the following will be collected if assessed:

1. Review and record adverse events
2. Review and record all concomitant medications
3. Assess adherence to Provant treatment regimen

4. Assess completion of the patient reported outcome form(s), as applicable
5. Conduct efficacy assessments:

Response to treatment with Provant will be determined based on the location of the subject's treatment area. Assessments will include the NPRS, CGI-I, PGIC and non-invasive assessments part of the Investigators standard of practice e.g., pain scores, SF-36, ankle-foot scales, oxygen perfusion (MOXY), and diaries with some subjects.

E. End of Treatment Visit

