All concomitant drug and non-drug treatments as well as the frequency of administration and indication for the treatment will be recorded in the subject's chart. Based on the subject's pain etiology, the investigator may disallow certain concomitant medications in order to accurately assess the effect of Provant therapy. Opioid or other pain drug therapies may be reduced or discontinued during the treatment period of the study as directed by the subject's treating physician.

It is important to record the reason why each analgesic medication is being taken by the subject, specifically analgesics taken for treatment of pain/edema. In this context, "analgesic medications" refers to medications prescribed and administered for the treatment of pain, and includes but is not limited to opioids, nonsteroidal anti-inflammatory agents, anti-depressants and muscle relaxants.

Prohibited Medications/Treatments

The following medications and therapeutics are prohibited throughout the study:

- Systemic steroids or topical steroids on the treatment location
- Transcutaneous electrical neurostimulators (TENS units)
- Implanted neurostimulators
- Local injections
- Intrathecal infusion
- Acupuncture
- Surgery

V. WITHDRAWAL PROCEDURES

If a subject or the prescriber decides to discontinue the subject's treatment with the device, efforts will be made to perform all assessments scheduled for the End of Treatment Visit prior to subject withdrawal.

VI. STATISTICAL CONSIDERATIONS

The statistical analysis of the study is described in detail in a separate version-controlled Statistical Analysis Plan (SAP). However, the statistical methodology described in this section of the protocol will be the basis for the detailed SAP.

Where not otherwise specified, the last pre-treatment observation will be used as baseline for calculating post-treatment changes from baseline. All confidence intervals will use a significance level of 5%.

A. Study Populations

Safety summaries will be conducted on all subjects who undergo treatment.

The effectiveness summaries will also be conducted on all subjects who undergo treatment. Subjects that do not attend the End of Treatment Visit will be excluded from the End of Treatment analyses. Subjects who complete the End of Treatment Visit will be assessed for efficacy regardless of the number of days of treatment received. No imputation of data will occur.

B. Efficacy Data Summaries

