Demographic and subject characteristics will be summarized using descriptive statistics. Assessments that are measured on a continuous scale will be summarized descriptively using the mean, standard deviation, median, minimum, and maximum value by time. Variables that are measured on a categorical scale will be summarized as a proportion of the population.

The change from baseline will be summarized for effectiveness outcome assessments in common between subjects/sites and 95% confidence intervals constructed.

Adverse events will be summarized using MedDRA categories and by severity and relationship. Concomitant medications will be summarized by WHODrug categories.

C. Adverse Events

All adverse events will be coded according to Medical Dictionary for Regulatory Activities (MedDRA). Safety assessments will include treatment-emergent adverse events (TEAEs; adverse events that occur in subjects who undergo treatment). Subjects with TEAEs will be summarized with frequencies and percentages by system organ class and preferred term, severity, and relationship to treatment for each treatment group. Treatment-related adverse events will be defined as adverse events with investigator assessment of related or possibly related. In summaries of TEAEs by severity and relationship to study device, subjects reporting multiple episodes will be counted once under the worst severity and the strongest relationship, respectively. Serious Adverse Events will also be presented by relationship to treatment.

The number of subjects with at least one adverse event will be tabulated. The number of adverse events will also be tabulated. The number of subjects and the number of adverse events will be tabulated by severity and relationship.

D. Sample Size

This is an open-label, non-controlled study with no formal hypothesis testing planned. It is anticipated that up to 300 subjects will be enrolled in this study. Data from this study will be included in a patient registry. The statistical analysis plan for the patient registry will fully describe the methods used to evaluate data from this study.

VII. INFORMED CONSENT

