APPENDIX A - TIME AND EVENTS SCHEDULE

Period	Screening Visit	Enrollment (Baseline) Visit ¹	Treatment Period	Interim Visits	End of Treatment Visit	Follow-up Phone Call
Study Day	-14 to 0	0	As Prescribed	As Prescribed	As Prescribed	3 months post-treatment
Informed Consent	X					
Demographic Information	X					
Medical/Surgical History	X					
Urine Pregnancy Test ²	X					
Height and Weight	X				X ⁷	
Inclusion/Exclusion Criteria	X	X				
Efficacy Outcomes Assessments (Including NPRS, CGI-I and PGIC)		X ³		X ³	X ³	X ³
Study Device Training		X ⁴				
Dispense Study Device		X				
Distribute Diary Collection Tool(s)		X ⁵				
Study Device Treatment			X ⁶			
Assess Adverse Events and Concomitant Medications	X ⁸	X		X	X	
Assess Subject Adherence to Treatment				X	X	
Collect Diary Collection Tool(s)				X	X	
Return Study Device and Unused DACs					X ⁹	

1. The Screening Visit and the Enrollment Visit may occur on the same day in which case none of the screening tests need to be repeated.
2. Urine pregnancy test will be performed on women of child-bearing potential.
3. The CGI-I and PGIC will not be conducted at the Enrollment (Baseline) Visit. Only the NPRS will be captured at the Follow-up phone call.
4. Introduction to and training on the study device will be completed during the Enrollment Visit.
5. Distribution of a diary collection tool will occur if the investigator decides to use this as a means for capturing patient reported outcomes. Completion of the forms will occur as instructed by the investigative site, as applicable.
6. The subject will self-administer treatments as prescribed by the investigator.
7. Collect only weight at End of Treatment Visit.
8. Assessment of adverse events will be conducted after the signing of the Informed Consent.
9. At the End of Treatment Visit subjects will return the study device and all unused Disposable Applicator Covers (DACs).

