- All summary tables will include the analysis population sample size (i.e., number of subjects).
- Study Day 1 is defined as the day the subject receives their initial exposure to the study device. All *study days* are determined relative to the day of initial treatment with the study device.
- Baseline values will be defined as those values recorded closest to, but prior to, the first study treatment.
- Change from baseline will be calculated as follows:
  - $Change = Post\text{-}baseline\ value - baseline\ value.$
- Date variables will be formatted as DDMMYYYY for presentation.
- Tables, figures, and listings will be presented in landscape orientation.

- SAS® Version 9.2 or higher will be the statistical software package used for all data analyses.
- All data from this study will be presented in listings. All listings will be sorted by subject number and visit date, as applicable.
- Table and listing numbering will follow ICH guidelines for post-text table and listing numbering.

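### No pain score is taken before washout of prohibited treatments, so a withdrawal rise that later reverses would count as improvement on Provant

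*Protocol*

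**What the plan says.** Washout is mentioned once, at the end of the Screening procedures in Protocol IV.A: "If subject does not require any washout for prohibited medications or procedures, the Screening Visit and the Enrollment Visit can be conducted concurrently". No duration, list of treatments or procedure is given. The only bound is the screening window: "The Screening Visit will take place no more than 14 days prior to the Enrollment Visit".

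The prohibited list in Protocol IV.I covers systemic steroids, topical steroids at the treatment site, TENS, implanted neurostimulators, local injections, intrathecal infusion, acupuncture and surgery. They are barred for the whole study. Ordinary analgesics are not on the list, although the investigator may disallow some medications according to etiology.

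None of the seven Screening procedures in IV.A is a pain score, and the efficacy row is blank under Screening both in Protocol Appendix A and in the SAP schedule (section 5). Pain is first scored at the Enrollment Visit (Protocol IV.B, item 5: "Conduct baseline efficacy assessments").

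That score becomes the baseline. Protocol VI says that "the last pre-treatment observation will be used as baseline for calculating post-treatment changes from baseline", and SAP section 7 agrees: "Baseline values will be defined as those values recorded closest to, but prior to, the first study treatment". Effectiveness rests on change from it: "The change from baseline will be summarized for effectiveness outcome assessments in common between subjects/sites and 95% confidence intervals constructed" (Protocol VI.B). There is no control arm.

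**The concern.** For a subject who stops TENS or acupuncture after Screening, the Enrollment score reflects pain shortly after withdrawal, at most 14 days later. If pain rose on stopping, the rise is already in the baseline. Should it then subside during up to 20 weeks of treatment, the fall enters the mean change as improvement. In a controlled trial a comparison arm would carry the same artefact. Here nothing does.

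No planned output would reveal it:

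- The Level 2 tables split subjects by reason for enrollment (pain, edema or both), and SAP 7.4 looks only at the condition treated.
- Baseline adjustment under SAP 7.1 uses the same post-washout value.
- The SAP's concomitant-treatment fields (3.2.3) and Listing 16.2.14 describe medications only, so they would not pick out someone who stopped a non-drug therapy.

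The study is meant to show how far PEMF contributes to pain management (SAP 3.1), and that rests entirely on change from baseline.

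**Working it through.** The plan gives no effect size, standard deviation or washout frequency, so there is no figure of its own to reproduce. The check has two parts.

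**When does the artefact arise?**

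| After a rise on withdrawal | Later score compared with baseline | Effect on mean change |
|---|---|---|
| Treatments stay off, rise persists | Both off treatment, both raised | None |
| Rise is a temporary flare, or pain is unstable at Day 0 | Later score lower without any device effect | Counted as improvement |
| Treatment is resumed | Later score lower because of the other treatment | Counted as improvement |

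The third route is most open at the 3-month call. Only the NPRS is taken there (Protocol IV.F; Appendix A, note 3), concomitant treatments are not scheduled for collection, and the documents do not say whether the prohibition still applies.

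**How large could it be?**

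Shift in mean change = f × r × q, where

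- f is the share of subjects washed out, assumed 0.10 to 0.30;
- r is the mean NPRS rise on withdrawal, assumed 0.5 to 2.0 points;
- q is the fraction of that rise that has reversed by the later visit, from 0 to 1.

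| q | Smallest shift (f = 0.10, r = 0.5) | Largest shift (f = 0.30, r = 2.0) |
|---|---|---|
| 0 | 0 | 0 |
| 0.5 | 0.10 × 0.5 × 0.5 = 0.025 | 0.30 × 2.0 × 0.5 = 0.30 |
| 1 | 0.10 × 0.5 × 1 = 0.05 | 0.30 × 2.0 × 1 = 0.60 |

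The yardstick is the 95% CI half-width for the mean change, 1.96 × SD / √n, with SD of change assumed 2.0 to 2.5. Both enrollment figures are used: up to 300 (Protocol VI.D) and 200 (SAP 4.3).

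- n = 300: 1.96 × 2.0 / √300 = 0.226; 1.96 × 2.5 / √300 = 0.283.
- n = 200: 1.96 × 2.0 / √200 = 0.277; 1.96 × 2.5 / √200 = 0.346.

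With 10% washed out, the largest shift is 0.10 × 2.0 × 1 = 0.20, below every half-width. Reaching 0.283 with full reversal needs about 0.283 / 0.20 = 1.4 points at 20% washed out, or 0.283 / 0.30 = 0.94 points at 30%. With half reversal, the top of the range (0.30) exceeds both half-widths at n = 300, but at n = 200 it exceeds only the one for SD 2.0.

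**The case against.** The strongest reply is that a post-washout baseline is the right comparator. The listed treatments are barred during the study, so baseline and on-treatment scores are both meant to be taken without them. A reader might infer that any rise on withdrawal is automatically credited to the device. The documents do not support that: a sustained rise produces no bias, and nothing in them shows that the rise reverses. This stands, and it is why q belongs in the formula.

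The affected group may also be small. Recent systemic corticosteroid use, implanted neurostimulators and anticipated surgery are already exclusions (Protocol III.D.2), and ordinary analgesics are not on the prohibited list. This stands in part. TENS, acupuncture, local injections, intrathecal infusion and topical steroids remain, and the SAP's baseline pain form (3.2.1) lists TENS and acupuncture among therapies that relieve pain, so some users are expected.

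A reader might also infer that washout subjects could never be identified, or that a subject who merely returns to pre-washout pain would be classed as a responder. Neither follows. Drug and non-drug treatments are to be recorded in the chart (Protocol IV.I) and medication stop dates are listed, so some washout subjects could be traced. No responder is defined in either document. What cannot be recovered is the pre-washout pain score.

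Finally, one Screening score cannot tell a temporary flare from a sustained rise. A change measured from Screening compares pain on the previous therapy with pain on Provant without it, which would understate the device effect if the rise persists. This stands, and it limits how the added row may be labelled. Where the two visits are combined, the extra score adds nothing.

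**Conclusion.** The point holds conditionally. Pain is not scored before washout, the post-washout value is the baseline, and no planned table separates washout subjects. A withdrawal rise that later reverses would therefore be counted as improvement on Provant and could not be separated out. If the treatments stay off and the rise lasts, there is no bias.

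On the assumed inputs the shift runs from 0 to 0.60 NPRS points. The upper figure is a ceiling that needs 30% of subjects washed out, a 2-point rise and full reversal. Against half-widths of 0.23 to 0.35 it may be negligible or may exceed the stated uncertainty. The share, rise, reversal fraction and SD are all assumptions, and the documents give no anchor for them. In a descriptive study without hypothesis testing this is a cheap improvement worth making, not a flaw that invalidates the results. It should be made before subjects are screened, because the missing score cannot be obtained later.

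**What to change.** **Protocol.** Add the NPRS, with the same question as at Enrollment, to the Screening list in IV.A and to the Screening column of Appendix A. On the case report form, flag each subject who stopped a prohibited drug or non-drug treatment between Screening and Enrollment, and record what was stopped and when. Keep the Enrollment score as the baseline.

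**SAP.** In Table 14.4.2.2, add two supportive rows:

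- (a) the mean change from the Enrollment baseline excluding washout subjects, as the main sensitivity check;
- (b) for washout subjects, the Screening and Enrollment scores and the change from Screening, labelled as a comparison with pain on previous therapy and not as a bias-corrected Provant effect.

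**Cost.** One 0–10 question at a visit that already takes place, one flag with its details, and two table rows. A small washout subgroup will give imprecise estimates in row (b). No change to the washout or prohibited-treatment rules is proposed.
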